8.1 Analysis of Primary Endpoints

The primary endpoint ORR and its corresponding 95% CI will be reported by cohorts and combined cohorts specified in Section 4.3. The primary endpoint ORR is the proportion of subjects who have achieved a CR or PR during the study.

Sensitivity analysis will be conducted for ORR excluding response data after the initiation of any non-protocol anti-underlying disease therapies.

CCI
[REDACTED]

8.2 Analysis of Secondary Endpoints

8.2.1 Overall Survival

Overall survival is defined as the time from the first dose of tablecleucel to the date of death for any cause. Subjects who are lost to follow-up or still alive will be censored on the last known-to-be-alive date. All data including those collected during the follow-up period, if any, will be summarized.

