2.4 Source of Study Treatment

As specified in Section 2.2, study treatment administered to subjects in this study included the following 3 types of EBV-CTL products.

2.4.1 *Third-party Cytotoxic T Lymphocytes*

Tabelecleucel, or third-party EBV-CTLs, refer to EBV-targeted CTLs generated from high resolution HLA-typed, EBV-seropositive, unrelated third-party donor T cells: ie, CTLs generated from a donor other than the subject's original allogeneic SOT or HCT transplant donor.

In this study, subjects could change to tabelecleucel with a different HLA restriction from a different donor either due to a lack of efficacy from the current cell line or insufficient supply.

Only the change to tabelecleucel with a different HLA restriction due to lack of efficacy is considered as treatment switch ("Restriction Switch")

2.4.2 *Transplant donor derived Cytotoxic T Lymphocytes*

Transplant donor-derived EBV-CTLs refers to T cells generated from the subject's original allogeneic SOT or HCT donor.

2.4.3 *Autologous Cytotoxic T Lymphocytes*

Autologous EBV-CTLs refers to T cells generated from the subjects themselves.

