4.1 Full Analysis Sets

The Full analysis set is defined as all subjects who received at least 1 dose of study treatment. All efficacy and safety analyses will use the full analysis set except for the endpoints of DOR and TTR, which will be conducted on the subjects in the full analysis set with an objective response (CR or partial response [PR]).

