4.2 Subject Cohorts

Analysis cohorts are defined based on subjects' disease background, prior EBV⁺ disease therapy, and source of study treatment received (as defined in Section 2.4). The cohort definitions are specified in [Table 1](#). With respect to prior EBV⁺ disease therapy, subjects with prior rituximab therapy data reported will be assigned to the relevant refractory/relapsed (R/R) rituximab cohort; subjects with no prior rituximab therapy data reported will be assigned to the rituximab-naïve cohort.

All analyses will be presented by the cohorts and combined cohorts defined in this SAP, not by the groups defined in the protocol. Cohorts to be used in the analysis depend on the data availability.

Table 1: Cohorts

Cohort Number	Cohort Name	Subjects Enrolled in The Study
1	Tab-cel HCT EBV ⁺ PTLD R/R Rituximab	Y
2	Tab-cel HCT EBV ⁺ PTLD Rituximab Naïve	Y
3	Tab-cel SOT EBV ⁺ PTLD R/R Rituximab	N
4	Tab-cel SOT EBV ⁺ PTLD R/R Rituximab + Chemo	Y
5	Tab-cel AID LPD	Y
6	Tab-cel PID LPD	Y
7	Tab-cel Lymphoma	N
31	Tab-cel LMS	Y
32	Tab-cel NPC	Y
61	Tab-cel Other Solid Tumor	N
71	Tab-cel Viremia	N
101	EBV-CTL (Transplant donor derived) HCT EBV ⁺ PTLD R/R Rituximab	Y
102	EBV-CTL (Transplant donor derived) HCT EBV ⁺ PTLD Rituximab Naïve	Y
103	EBV-CTL (Transplant donor derived) SOT EBV ⁺ PTLD	Y
106	EBV-CTL (Transplant donor derived) PID LPD	Y
107	EBV-CTL (Transplant donor derived) Lymphoma	Y
171	EBV-CTL (Transplant donor derived) Viremia	Y
201	Autologous	Y

Abbreviations: AID, acquired immunodeficiency; chemo, chemotherapy; CTL cytotoxic T lymphocyte; EBV, Epstein-Barr virus; HCT, hematopoietic cell transplant; LPD, lymphoproliferative disorder; N, no; NPC, nasopharyngeal carcinoma; PID primary immunodeficiency; post-transplant lymphoproliferative disorder; R/R, refractory/relapsed; SOT, solid organ transplant; tab-cel, tablecleucel; Y, yes

Disposition, demographics, baseline characteristics, exposure and safety will be summarized as in the following headers:

Table a: HCT Cohorts:

Tab-cel HCT EBV+ PTLD				EBV-CTL (Transplant donor derived)			Total (cohort 1, 2, 101, 102)
R/R	Rituximab	R/R	Rituximab	Naïve	Total		
Rituximab (cohort 1)	Naïve (cohort 2)	Total (cohort 1+2)	(cohort 101)	Naïve (cohort 102)	Total (cohort 101+102)		

Table b: *SOT Cohorts*:

Tab-cel SOT EBV+ PTLD R/R Rituximab+Chemo (cohort 4)	EBV-CTL (Transplant donor derived) SOT EBV+ PTLD (cohort 103)	Total (cohort 4+103)
--	---	-------------------------

Table c: *Other cohorts and All cohorts*:

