Other EBV+ Disorders with ID	HCT/SOT EBV+ PTLD	EBV+ Malignancy without ID
		EBV-CTL Tab-cel
		(Transplant donor derived) NPC Total (cohort 32) (cohort 107+32)
	Total	Lymphoma
AID LPD PID LPD Viremia LMS (cohort 5, (cohort 1,2,101,102, (Cohort 107)	(cohort 6+106, (cohort 106, 101, 102, 103)	Total (all cohorts)
(cohort 5) 6+106) 171) 31) 171, 31) 4, 103) 107)		

Table d: *Other cohorts and All cohorts – tabelecleucel only*:

Other EBV+ Disorders with ID	HCT/SOT EBV+ PTLD	EBV+ Malignancy without ID
		Tab-cel Total
AID PID LMS (cohort 1,2, (cohort 101,102, (Cohort 1+2) (Cohort 4) (cohort 1,2,4) Tab-cel Total (cohort 5) LPD LPD (cohort 31) 4, 103) (Cohort 103) (Cohort 4) 32) (all cohorts)	HCT EBV+ SOT EBV+ Total NPC (cohort 32) (cohort 1,2,4) 32) tab-cel	

Efficacy will be summarized as in the following headers:

Table a: HCT Cohorts:

Tab-cel HCT EBV ⁺ PTLD				EBV-CTL (Transplant donor derived)			
R/R	Rituximab	R/R	Rituximab	EBV ⁺ PTLD	Total	(cohort	Total
Rituximab	Naïve	Total	Rituximab	Naïve	(cohort	(cohort 1)	(cohort 102)
(cohort 1)	(cohort 2)	(cohort 1+2)	(cohort 101)	(cohort 102)	101+102)		

Table b: *SOT Cohorts:*

Tab-cel SOT EBV ⁺ PTLD R/R	EBV-CTL (Transplant donor derived) SOT EBV ⁺ PTLD
Rituximab+Chemo (cohort 4)	(cohort 103)

Table c: *Other cohorts and All cohorts:*

Other EBV ⁺ Disorders with ID				EBV ⁺ Malignancy without ID		
AID	PID	Viremia	LMS	EBV-CTL (Transplant donor derived)	Lymphoma	Tab-cel NPC
LPD (cohort 5)	(cohort 6+106)	(cohort 171)	(cohort 31)	(Cohort 107)		(cohort 32)

Table d: *Other cohorts and All cohorts – tabelecleucel only:*

Other EBV ⁺ Disorders with ID				EBV ⁺ Malignancy without ID
AID (cohort 5)	PID (cohort 6)	Viremia (cohort 31)	LMS (cohort 31)	Tab-cel NPC (cohort 32)

Cohort Assignment for Subjects with > 1 Source of Study Treatment

Some subjects may receive EBV-CTLs from > 1 donor source type (Section 2.4) during the study. As a general rule for efficacy analysis, any transplant donor-derived or autologous EBV-CTL treatment received after the initiation of tabelecleucel will be considered as other anti-underlying EBV⁺ disease therapy. For such subjects, the efficacy analysis may be censored due to the initiation of this therapy in sensitivity analysis.

The efficacy and safety data for a subject who starts with tabelecleucel and then switches to either transplant donor-derived or autologous EBV-CTLs will be presented under the relevant tabelecleucel cohort.

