Each subject who first receives an EBV-CTL product other than tabelecleucel and then switches to a different non-tabelecleucel EBV-CTL product (eg, transplant donor-derived followed by autologous) will be considered as 2 independent subjects for the purposes of analysis. The efficacy and safety data for such a subject will be assigned to the relevant study treatment source cohort based on the initial dose of each product type.

A subject who first receives an EBV-CTL product other than tabelecleucel, switches to tabelecleucel, and then switches to a non-tabelecleucel EBV-CTL product, will be considered as 2 independent subjects, based on the first 2 study treatments received, for the purposes of analysis. The efficacy and safety data for such a subject will be assigned to the relevant study treatment source cohort based on the initial dose of the first 2 product types. The third EBV-CTL product will be considered as other anti- post-transplant lymphoproliferative disorder (PTLD) therapy.

Data for subjects assigned to the autologous EBV-CTL cohort will not be included in the summary tables or figures. The efficacy and safety data for these subjects during autologous EBV-CTL treatment will be provided in the listings.

Regardless of the number of products received, all subjects will be counted only once in the ‘Overall Total’ combined cohort for safety analyses.

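### OS, time to response, one PFS sensitivity analysis and the clinical benefit threshold are dated from the first tabelecleucel dose, which donor-derived-only subjects never received; exposure duration and the treatment-emergent laboratory window carry the same wording

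*SAP*

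**What the plan says.** SAP 8.2.1 sets the origin of survival: "Overall survival is defined as the time from the first dose of tablecleucel to the date of death for any cause" (the product name is misspelled there; nothing turns on that). SAP 8.2.6 starts time to response at the same dose. So does the sensitivity analysis in 8.2.3 that takes the first progression as the event. SAP 8.2.4 uses the same date as the 28-day reference for clinical benefit.

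SAP 2.4.1 fixes what the product is: "Tabelecleucel, or third-party EBV-CTLs, refer to EBV-targeted CTLs generated from high resolution HLA-typed, EBV-seropositive, unrelated third-party donor T cells". Transplant donor-derived and autologous cells are separate products in 2.4.2 and 2.4.3.

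The population is wider. SAP 4.1: "The Full analysis set is defined as all subjects who received at least 1 dose of study treatment", and "All efficacy and safety analyses will use the full analysis set except for the endpoints of DOR and TTR", those two being run on the responders within it. SAP 4.2: "All analyses will be presented by the cohorts and combined cohorts defined in this SAP, not by the groups defined in the protocol". Only the autologous cohort is kept out of tables and figures.

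For subjects given more than one product, 4.2 keeps a subject "who starts with tabelecleucel and then switches to either transplant donor-derived or autologous EBV-CTLs will be presented under the relevant tabelecleucel cohort". A subject who moves between two non-tabelecleucel products becomes two records, each "assigned to the relevant study treatment source cohort based on the initial dose of each product type". One who goes from another product to tabelecleucel and then to a third product "will be considered as 2 independent subjects, based on the first 2 study treatments received, for the purposes of analysis".

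**The concern.** A subject treated only with donor-derived cells belongs to the analysis set and to a reported cohort, but has no first tabelecleucel dose. The programmer must then either choose an origin that the SAP does not give, or leave OS and time to response blank in cohorts where ORR, primary PFS and TTP can be computed. OS is also repeated by subgroup under 8.3, so the gap carries over.

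Subjects who change product raise a second problem. If a donor-derived record is followed by tabelecleucel, the literal text dates that record's OS and time to response from the later product.

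The safety sections show the same slip. Section 7.4 measures exposure between tabelecleucel doses where 6.1 says study treatment. Section 10.2.2 closes the treatment-emergent laboratory window by the last tabelecleucel dose where 10.2.1 uses the last study treatment dose.

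**Working it through.** The plan states no figure to reproduce. The check sets the definitions side by side, counts cohorts, and works one example.

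**1. Reference dates**

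| Quantity | SAP section | Reference |
|---|---|---|
| OS | 8.2.1 | first tabelecleucel dose |
| Time to response | 8.2.6 | first tabelecleucel dose |
| PFS sensitivity, first progression | 8.2.3 | first tabelecleucel dose |
| Clinical benefit, 28 days | 8.2.4 | first tabelecleucel dose |
| Primary PFS | 8.2.3 | first study treatment |
| TTP | 8.2.5 | first study treatment |
| Day 1, baseline | 6.1 | first study treatment |
| DOR, DRR | 8.2.2, 8.2.4 | the response |

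Of the six secondary endpoints in 3.2, two (OS, time to response) use tabelecleucel, two (PFS, TTP) use study treatment and two (DOR, DRR) run from the response. The PFS sensitivity analysis claims to keep every other detail of the primary analysis, including a death rule tied to the first study treatment date, yet it names a different start dose.

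**2. Cohorts reached (SAP 4.2, Table 1)**

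- Marked as enrolled: 7 tabelecleucel (1, 2, 4, 5, 6, 31, 32), 6 donor-derived (101, 102, 103, 106, 107, 171) and 1 autologous (201, listings only).
- Tabulated enrolled cohorts: 7 + 6 = 13. Donor-derived share: 6/13 = 46% of cohorts.

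**3. Worked example, tabelecleucel first.** Assumptions: nominal schedule from protocol Treatment Plan VI (days 0, 7 and 14, then at least 3 weeks of observation); one tabelecleucel course; a switch at the earliest nominal date; one donor-derived course; the 3-day tolerance ignored.

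- Last tabelecleucel dose: day 14. The 10.2.2 window ends at 14 + 30 = day 44.
- Donor-derived course starts at 14 + 21 = day 35; its last dose is 35 + 14 = day 49.
- The 10.2.1 window, and the 30-day limb of the 10.1 SAE definition, end at 49 + 30 = day 79.
- Gap: 79 − 44 = 35 days.
- Exposure duration: 14 − 0 + 1 = 15 days under 7.4, against 49 − 0 + 1 = 50 days under 6.1.

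For a donor-derived-only subject, 10.2.2 has no end date at all.

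**4. Reverse order, same schedule.** With donor-derived cells on days 0, 7 and 14 and tabelecleucel from day 35, the donor-derived record's OS would start on day 35. A response dated before day 35 would give a negative time to response. In the tabelecleucel record, PFS read from the first study treatment ever given starts on day 0 and OS on day 35.

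**The case against.** The strongest reply is that the intent is plain. Section 6.1 counts time on study from the first study treatment, primary PFS and TTP follow it, and 4.2 assigns records by initial dose. A competent programmer would use the first dose received, and for a donor-derived-only subject every sensible reading gives that date. This shows the probable intent, and it stands as a reason for low severity. It does not override four explicit definitions, and it does not settle subjects with two records, for whom first study treatment and first dose of the cohort's product differ. Nor is tabelecleucel a synonym for study treatment: 4.2 contrasts it with other EBV-CTL products and has tabelecleucel-only table headers. The remark in 4.2 that the cohorts used depend on available data might excuse a missing column; it supplies no date.

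A reader might also infer more than the documents support:

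- *That clinical benefit cannot be computed.* It is a proportion that lacks a day-28 reference. If the 28-day condition applies only to SD, CR and PR can still be classified.
- *That SAE counting stops on day 79 in the example.* SAP 10.1 also counts related SAEs from the first dose onward with no end date; only its 30-day limb closes then.
- *That 46% of subjects are affected.* The figure counts cohorts. Neither cohort sizes nor the number of switchers is given.
- *That the efficacy results as a whole are undermined.* ORR is the primary endpoint and does not use this anchor.

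**Conclusion.** The definitions are wrong as written, and the consequence is minor. For donor-derived-only subjects, OS, time to response and one PFS sensitivity analysis have no origin, clinical benefit has no 28-day reference, and the treatment-emergent laboratory window has no end. For a donor-derived record followed by tabelecleucel, the literal origin is too late. Exposure duration is a conflict between 7.4 and 6.1.

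The scope is six of 13 tabulated enrolled cohorts and two of six secondary endpoints; the effect on any estimate cannot be computed. The 35-day laboratory gap holds only under the assumed switch, and a longer rest or further donor-derived courses would widen it. ORR, DOR, DRR and subjects given only tabelecleucel are unaffected, and SAP 11 plans estimates with intervals and no formal test on CR.

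**What to change.** 1. In 8.2.1, 8.2.4 (clinical benefit), 8.2.6 and the 8.2.3 first-progression sensitivity analysis, replace the first tabelecleucel dose with the first dose of the study treatment that defines the subject's cohort record, following the initial-dose rule in 4.2. Say in 8.2.4 whether the 28-day condition applies to SD only.
2. In 7.4 and 10.2.2, replace tabelecleucel with study treatment for that cohort record, consistent with 6.1 and 10.2.1.
3. State that first study treatment in primary PFS and TTP means the same record-level date. This is a real change for subjects who switch and hold two records: the second record's origin moves from the first study treatment ever given to the first dose of the second product (day 0 to day 35 in the reverse-order example).
4. State in 4.2 that a simple move from donor-derived cells to tabelecleucel creates two records; this is implied but not said.
5. State that a subject with two records is counted once in any combined efficacy column, such as 6+106, and which record supplies the entry. The count-once rule in 4.2 covers only the safety overall total, so one death could otherwise be counted twice.
6. Keep the OS event and censoring rules of 8.2.1, and do not apply the Section 10 safety cut-off to OS.

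The cost is SAP wording, one derived start date per cohort record, and one stop date for exposure and laboratory data. No new data are needed, and results for subjects given only tabelecleucel do not change.

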8.2.2 Duration of Response

Duration of response is calculated based on subjects who achieve CR or PR. DOR is defined as the time from the date of initial response until (1) progression after the last response or (2) death due to any cause.

Only deaths within 90 days after the last valid disease evaluation (ie, not NE) will be counted as events in the DOR definition above.

For subjects without an event of death or disease progression, DOR is censored at the last valid (not NE) disease evaluation date.

In a sensitivity analysis, if any anti-underlying disease therapy is initialized before the event date/censoring date, DOR is censored at the last assessment date prior to the therapy initialization.

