### **VIII. Post-Infusion Evaluation**

The evaluations below are approximate and will be performed as clinically necessary:

Patients will be evaluated by interval medical history and physical examination daily during the T-cell infusions. Vital signs will also be monitored prior to and at 1, 2, 4, and 24 hours following initiation of each infusion of EBV-specific T-cells. Thereafter, patients will be clinically evaluated at least weekly during the three week periods of observation following each course of infusions and, subsequently, at monthly intervals until 6 months post initial infusion. Patients achieving complete remission will be evaluated at six month intervals for one year thereafter, or more frequently as clinically indicated to assess duration of response. Patients achieving partial remissions or stable disease three weeks following the second course of T-cell infusions will be closely followed until first evidence of further progression, at which time alternative therapies may be initiated. Patients exhibiting disease progression within three weeks after the second course of T-cell infusions may also be considered for alternative treatments.

Patients will also be assessed for the effects of the adoptively transferred EBV-specific T-cells or circulating levels of EBV DNA. For these studies, heparinized blood (10cc) will be drawn on days 1, 7, 14, 21, and 28 post-T-cell infusion and, monthly thereafter for four months. Isolated PBMC will be assayed for EBV DNA copy number, using a standard quantitative PCR amplified assay, (59).

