8.2.3 Progression-free Survival

Progression-free survival is defined as the time from the first dose of study treatment to either of following events whichever occurs first: (1) progression after the last response or (2) death due to any cause.

Death within 90 days after last valid disease evaluation (ie, not NE), or first study treatment dose date if there is no valid post-baseline disease evaluation, will be counted as events in the PFS definition

For subjects without an event as defined above, PFS will be censored at

- Last valid (not NE) post -baseline disease evaluation date
- First dose date if there is no valid post-baseline disease evaluation.

As a sensitivity analysis, PFS will be defined as the time from the first dose of tabelecleucel to either of following events, whichever occurs first, (1) the first progression or (2) death due to any cause. All other details and censoring rules are the same as above for the primary PFS analysis.

In another sensitivity analysis, if any anti-underlying disease therapy is initialized before the event date/censoring date, PFS is censored at the last assessment date prior to the therapy initialization.

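### The 90-day limit on counting deaths in DOR and PFS is shorter than the six-month visit interval planned for complete responders, and no visible sensitivity analysis lifts it

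*SAP*

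**What the plan says.** SAP 8.2.2 ends DOR at progression or at death from any cause, and then adds: "Only deaths within 90 days after the last valid disease evaluation (ie, not NE) will be counted as events in the DOR definition above". The censoring rule follows: "For subjects without an event of death or disease progression, DOR is censored at the last valid (not NE) disease evaluation date". A death outside the window is not an event, so it falls under that rule.

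SAP 8.2.3 does the same for PFS. The limit reads "Death within 90 days after last valid disease evaluation (ie, not NE), or first study treatment dose date" (the dose date applies when there is no valid post-baseline evaluation). The censoring rule, "For subjects without an event as defined above, PFS will be censored at", then points to the last valid evaluation.

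Three sensitivity analyses are visible for these endpoints:
- PFS to first progression, for which "All other details and censoring rules are the same as above for the primary PFS analysis".
- PFS censored at the start of another anti-disease therapy.
- DOR censored at the start of another anti-disease therapy.

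Protocol section VIII, Post-Infusion Evaluation, plans clinical evaluation "at monthly intervals until 6 months post initial infusion". After that, "Patients achieving complete remission will be evaluated at six month intervals for one year thereafter", or more often if clinically needed.

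Overall survival (SAP 8.2.1) counts every death with no window: "Subjects who are lost to follow-up or still alive will be censored on the last known-to-be-alive date".

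**The concern.** The window is about half the planned gap between visits for complete responders after month 6. A patient can keep every planned appointment, die in response, and be recorded as censored at a visit months earlier.

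Death itself triggers that censoring. Kaplan-Meier, which SAP 6.1 specifies, assumes that censoring carries no information about the event, so the assumption fails for these patients. DOR and PFS are the secondary endpoints that describe how long benefit lasts. As planned, a reader could not tell whether those estimates depend on deaths that the rule leaves out, or how many such deaths there were.

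**Working it through.** **Inputs.** The window is 90 days (SAP 8.2.2 and 8.2.3). One month is 365.25/12 = 30.44 days (SAP 6.1). Planned visits for complete responders are monthly to month 6, then months 12 and 18 (protocol section VIII). The documents give no death rate. I assume 24-month survival of 80%, 70% or 50% with constant hazard, deaths only, planned visits only, and the clock starting at first dose.

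**1. Window against interval.**

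| Interval | Days | Share not covered by 90 days |
|---|---|---|
| 1 month | 30.4 | none |
| 6 months | 182.6 | 1 − 90/182.6 = 51% |

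The gap first opens at 182.6 + 90 = 272.6 days and lasts until the month-12 visit at 365.25 days. For example, a complete responder seen at month 6 who dies on day 300 died 300 − 182.6 = 117.4 days after the last evaluation. The death is not counted, and the patient is censored at about day 183.

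**2. Do the sensitivity analyses lift the limit?** The first-progression PFS analysis keeps the censoring rules explicitly. The two therapy-based analyses only add censoring. A redacted block in SAP 8.1 cannot be checked, but it sits under ORR.

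**3. Size if every survivor is evaluated at month 18.** This can be checked by hand. Let h = −ln(S24)/730.5 per day. Over a six-month interval, q = 1 − exp(−182.6h) is the probability of death, and c = 1 − exp(−90h) is the probability of a counted death. Uncounted deaths (q − c) leave the risk set at the visit, so each interval contributes 1 − c/(1 − (q − c)). No death is dropped in months 0 to 6, where the estimate is S24^0.25.

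For S24 = 0.70: q = 0.0853 and c = 0.0430, so the factor is 1 − 0.0430/0.9577 = 0.9551. The month-18 estimate is 0.9147 × 0.9551² = 0.834. The true value is 0.70^0.75 = 0.765.

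| S24 | 90-day rule, month 18 | True | Error (points) |
|---|---|---|---|
| 0.80 | 0.894 | 0.846 | +4.8 |
| 0.70 | 0.834 | 0.765 | +6.9 |
| 0.50 | 0.698 | 0.595 | +10.4 |

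**4. Size if follow-up ends are spread evenly over months 6 to 24.** This was simulated with millions of patients per scenario. Errors are in points for S24 = 80/70/50%, good to about 0.1.

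| Month | 90-day rule | All deaths counted |
|---|---|---|
| 9 | −1.0/−1.5/−3.0 | −1.0/−1.3/−2.3 |
| 12 | +1.5/+2.2/+3.5 | −1.2/−1.8/−2.7 |
| 15 | −0.4/−0.7/−1.5 | −2.9/−4.2/−6.0 |
| 18 | +2.0/+2.8/+3.8 | −3.4/−4.7/−6.7 |

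The rule drops 22–24% of deaths here. The sign changes because survivors whose follow-up ends between visits are also censored back at their last visit. That shrinks the risk set just after each visit, so the curve falls too fast for 90 days. It then stays flat until the next visit, because no death in that stretch counts.

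**5. More frequent visits.** With monthly evaluations no deaths are dropped. With three-monthly visits and spread-out ends, the two analyses nearly agree at month 18, and both err low by roughly 1 to 3 points.

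**The case against.** **The schedule is soft.** Protocol section VIII calls its evaluations approximate, lets complete responders be seen more often, and elsewhere moves patients to monthly tests and examinations once infusions end, with no end date there. SAP Table 2 accepts physical examination and laboratory results as assessment modalities, so an assessment based on one of these can restart the 90-day clock. This stands: actual evaluation dates decide the effect, and it may be nil. It does not show that the effect is nil, and the plan reports nothing that would let a reader see.

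**A window on late deaths is a legitimate choice.** It avoids crediting a long unassessed interval to response, and time to progression (SAP 8.2.5) uses it too. This also stands, and is why the 90-day analysis should remain.

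**The all-deaths analysis can be less accurate.** In the staggered case at month 18 it errs by −3.4/−4.7/−6.7 points, against +2.0/+2.8/+3.8 for the rule. This stands, and it limits what the added analysis may be said to show.

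**The consequence is small.** ORR, the primary endpoint, is untouched, OS counts every death, and SAP section 11 plans no formal test on CR. Even 47 uncensored patients in one cohort would give a 95% interval near 77% of ±1.96 × √(0.77 × 0.23/47) = ±12 points, and the SAP's cohorts split the patients further. This bears on priority. It does not remove the mismatch between window and interval.

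**Conclusion.** The point holds as a cheap improvement to secondary, descriptive endpoints. If evaluations follow the planned six-month interval, the 90-day limit turns some deaths of fully compliant complete responders into censored observations, and nothing visible in the SAP tests for this. The sizes above rest on assumed survival, constant hazard and planned visits only. If half the event hazard is progression, the staggered month-18 error falls to about +1.1/+1.5/+2.1 points. A cohort also mixes complete responders with other patients, so the figures for complete responders are an upper end for it.

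Three stronger readings are tempting and not supported:
- *That the rule biases DOR and PFS upward in general.* With spread-out follow-up the estimate is slightly low at months 9 and 15, and with monthly evaluation no deaths are dropped.
- *That the 90-day and all-deaths analyses bracket the true value.* At months 9 and 15 in the staggered case both err low.
- *That the limit undermines the durable response rate.* SAP 8.2.4 does not say how a response censored before six months is classified, but that applies equally to living responders. It is a separate gap, and the change proposed here does not fill it.

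Partial responders and patients with stable disease have a four-month follow-up interval (1 − 90/121.75 = 26% uncovered). The protocol also asks for close follow-up of them without stating an interval, so the conclusion does not rest on them.

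**What to change.** Add one sentence to SAP 8.2.2 and one to 8.2.3, for example: *As a sensitivity analysis, every death will be counted as an event on its date, whatever the time since the last valid evaluation, with all other rules unchanged; the number of deaths excluded by the 90-day limit will be reported for each cohort.*

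Keep the 90-day analysis and show the two side by side. Describe the addition as a check on whether the limit matters. It is neither a more accurate estimate nor one end of a bracket, because survivors are still censored at their last evaluation and the all-deaths result can err low. The count of excluded deaths needs no model and is informative either way: if it is zero or nearly so, the question is closed.

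The cost is two sentences, one extra run for each endpoint and one count per cohort. The death dates are already needed for OS, so no new data are required.
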